## 3.3.3 Risk Associated with Lack of Efficacy

No deterioration in health status is expected following the administration of IFX-1 in pyoderma gangrenosum. Nevertheless, deterioration can occur due to the fluctuating nature of the disease. In case of a lack of efficacy with IFX-1 treatment, subjects will continue to experience their typical symptoms.

## 3.3.4 Risk-Benefit Conclusion

It is hypothesized that treatment with IFX-1 could block the C5a-mediated inflammatory effect and support wound healing. Thus, reducing the pain and consequent physical impairment associated with the lesions of pyoderma gangrenosum, and even improving the disease status.

The hypothesized benefit of treatment with IFX-1, therefore, outweighs the potential risks for the subjects participating in this study.

More detailed information about the known and expected benefits and risks and reasonably expected adverse events of IFX-1 may be found in the investigator's brochure.

## **4 OBJECTIVES AND ENDPOINTS**

[figure not shown]
The objectives and endpoints are presented in the Synopsis (Objectives and Endpoints).

## 5 STUDY DESIGN

## 5.1 Overall Design

## Figure 1 Study Design

IFX-1

Note: last day of dosing of IFX-1 is on Day 169 Q2W = every 2 weeks

This is an open-label explorative study.

Subjects will be examined and receive IMP (IFX-1) according to the Schedule of Assessments (Section 2). IFX-1 will only be administered at a treatment visit.

After completion of treatment with IMP (last IMP is given on Visit V15), subjects should complete an EOT visit at Day (Visit V16). Subjects who discontinue early should, if possible, also complete the EOT visit. Thereafter, subjects should receive treatment for pyoderma gangrenosum at the discretion of the investigator.

Subjects will be followed up for an additional days after EOT at Visit Ob1 (after days) and Visit Ob2 (after 60 days) for safety reason. Visit Ob2 is the final visit in the study.

InflaRx	Clinical Study Protocol,
	Version 4.0 Including Amendment 02, 14 May 2020
IFX-1	IFX-1-P2.7

The allowed time windows for Visits V1 to V6 are  $\pm 2$  days. All other visits have allowed time windows of  $\pm 5$  days. There must be at least 48 hours between each dose of IFX-1 (Section 34). Visits should be scheduled appropriately.

# 5.2 Study Sites, Study Subject, and Expected Duration

This study is planned to be a multi-center study with about 18 subjects treated with IMP (IFX-1).

The study start is defined as the date of the first visit of the first subject enrolled (signature of the informed consent form by the first subject), and the end of the study is defined as the date of the last visit of the last subject participating, as recorded in the Case Report Form (CRF).

The estimated recruitment period is approximately 6 to 12 months.

The study duration for an individual subject includes screening (14 days range 7 to 35 days), the treatment period (189 days  $\pm$ 5 days; the last day of dosing of IFX-1 is Day 169), and the observational follow up (60 days  $\pm$ 5 days).

# 5.3 End of Study Definition

A subject is considered to have completed the study if all phases of the study have been completed including the last visit.

The end of the study is defined as the date of the last visit of the last subject in the study.

# **6 STUDY POPULATION**

## 6.1 Inclusion Criteria

The inclusion criteria are presented in the synopsis (Study Population Inclusion Criteria).

## 6.2 Exclusion Criteria

The exclusion criteria are presented in the synopsis (Study Population Exclusion Criteria).

## 6.3 Lifestyle Restrictions

## 6.3.1 Meals and Dietary Restrictions

No restrictions pertaining to meals and dietary restrictions apply during the study.

## 6.3.2 Caffeine, Alcohol, and Tobacco

No restrictions pertaining to caffeine, alcohol, or tobacco restrictions apply during the study.

InflaRx	Clinical Study Protocol,
	Version 4.0 Including Amendment 02, 14 May 2020
IFX-1	IFX-1-P2.7

## 6.3.3 Activity

Subjects will abstain from strenuous exercise for 2 hours before each blood collection for safety laboratory tests.

## 6.4 Screening Failures

Screening failures are defined as subjects who consent to participate in the clinical study but are not subsequently assigned to IMP in the study. A minimal set of screen failure information is required to ensure transparent reporting of screen failure subjects to meet the Consolidated Standards of Reporting Trials publishing requirements and to respond to queries from regulatory authorities. Minimal information includes demography, screen failure details, eligibility criteria, and any serious adverse event (SAE).

Individuals who do not meet the criteria for participation in this study (screening failure) may be re-screened once. Re-screened subjects will receive the next available subject number.

## 6.5 Gender distribution

The incidence of pyoderma gangrenosum is possibly higher in women (Chatzinasiou 2016, Langan 2012, Wollina 2007). It is expected that approximately twice as many women as men will be enrolled in this study.

## 7 TREATMENT WITH IMP AND CONCOMITANT THERAPY

## 7.1 Investigational Medicinal Product

Further guidance and information will be provided in a pharmacy manual describing IMP handling, storage and administration.

IMP name:	IFX-1
Unit dose strength(s)/ Dosage	mL glass vials at a concentration of
level(s):	
Route of administration:	Intravenous
Dosing instructions:	The required dose of IFX-1 will be diluted with sodium chloride
	to a total volume of approximately 250 ml and given as a single
	intravenous dose over minutes
Packaging and labeling:	The vials of IFX-1 will be labeled and packed in labeled
	cardboard cartons. Labeling will be in accordance with all legal
	requirements.
	The cartons will be labeled with a unique number (medication or kit
	number). The vials within a carton will be labeled with the same
	(medication) number as the carton in which they are packed
Manufacturer:	Celonics and WuXi on behalf of InflaRx

## 7.1.1 Treatment Administered

IFX-1 has the following composition:

InflaRx	Clinical Study Protocol,
	Version 4.0 Including Amendment 02, 14 May 2020
IFX-1	IFX-1-P2.7

Ingredient	Strength
IFX-1	
Sodium chloride	
Sodium phosphate	
Polysorbate 80	

#### 7.1.2 Dosing groups

There will be 3 dosing groups (Group 1, Group 2, and Group 3) of 6 subjects each. Each group of subjects is recruited sequentially. The next dose group will be initiated if the previous dose was considered safe and well tolerated. If dosing in Group 2 cannot be initiated, then a further 6 patients will be recruited in Group 1.

All subjects will receive IFX-1 800 mg three times during the first week (Days 1, 4, and 8).

Starting at Day 15:

- Subjects in Group 1 will continue to receive IFX-1 800 mg at 2 weekly intervals.
- Subjects in Group 2 will receive IFX-1 1600 mg at 2 weekly intervals.
- Subjects in Group 3 will receive IFX-1 2400 at 2 weekly intervals.

At Day 57 (Visit V7), subjects in Groups 1 and 2 may have their dose increased to IFX-1 1600 mg or 2400 mg, respectively, if there are no safety concerns and the Physician Global Assessment (main efficacy parameter) is  $\geq$ 4.

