#### **Treatment Groups and Duration:**

The estimated recruitment period is approximately 6 to 12 months.

If a subject discontinues the trial prematurely for any reason, they should have a termination visit (Visit V16 = EOT) and should be followed up at Visit Ob1 and Visit Ob2.

All subjects will receive IFX-1 at a maximum of 15 dosing visits.

There will be 3 dosing groups (Group 1, Group 2, and Group 3) of 6 subjects each. Each group of subjects is recruited sequentially. The next dose group will be initiated if the previous dose was considered safe and well tolerated. If dosing in Group 2 cannot be initiated, then a further 6 patients will be recruited in Group 1.

InflaRx	Clinical Study Protocol,
	Version 4.0 Including Amendment 02, 14 May 2020
IFX-1	IFX-1-P2.7

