## 8.1 Discontinuation of the Study

The study may be discontinued by the sponsor at any site if any of the following criteria are met:

- The study protocol is not adequately adhered to (protocol violations) despite training of the study site personnel
- The data quality is deficient
- The recruitment is inadequate

Additionally, the entire study can be discontinued at all sites by the sponsor at any time for medical or ethical reasons.

The investigator(s) will be notified in writing, outlining the reasons for discontinuation, and the investigator(s) must promptly inform all participating subjects. Detailed instructions on further assessments will be provided.

InflaRx	Clinical Study Protocol,
	Version 4.0 Including Amendment 02, 14 May 2020
IFX-1	IFX-1-P2.7

All study materials, except documents needed for archiving requirements, will be returned to the sponsor, including all records regarding the IMP, and the sponsor will decide on whether any unused IMP should be returned or destroyed. The sponsor or sponsor's designee will ensure that any outstanding data clarification issues and queries are resolved and that all study records at the study site are complete.

In accordance with applicable regulatory requirements, the sponsor or sponsor's designee will promptly inform the competent regulatory authorities of the discontinuation and its reason(s), and the investigator or sponsor or sponsor's designee will promptly inform the IRB.

The approval of the study can be rescinded, or the study can be discontinued by a competent authority or a responsible IRB.

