# 9.4.9 Safety review

An ongoing safety review will also be performed. The decision to go to the next dose group will be made by the sponsor. The decision to start dose Group 2 will be based on safety data from at least 5 patients on IFX-1 800 mg, and to start Group 3 on at least 5 patients on IFX-1 1600 mg for at least 1 month.

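### The rule adding 6 subjects at 800 mg if Group 2 cannot open makes no exception for 800 mg itself being judged unsafe

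*Combined protocol and SAP*

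**What the plan says.** The opening rule and the fallback stand next to each other, in the same words, in the synopsis (Treatment Groups and Duration) and in section 7.1.2.

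- Opening rule: "The next dose group will be initiated if the previous dose was considered safe and well tolerated". For Group 2, the previous dose is the 800 mg regimen of Group 1.
- Fallback: "If dosing in Group 2 cannot be initiated, then a further 6 patients will be recruited in Group 1". No qualifier follows.

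Section 9.4.9 bases the Group 2 decision on safety data from at least 5 patients on 800 mg and names who decides: "The decision to go to the next dose group will be made by the sponsor".

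Section 7.1.2 does attach a safety condition to a different step, the Day 57 increase for those in the two lower groups who score 4 or higher on the Physician's Global Assessment: they "may have their dose increased to IFX-1 1600 mg or 2400 mg, respectively, if there are no safety concerns".

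Stopping is dealt with elsewhere. Section 8.1 says: "Additionally, the entire study can be discontinued at all sites by the sponsor at any time for medical or ethical reasons". It also allows a competent authority or IRB to end the study. Appendix 2 (Study and Site Closure) reserves a general right of termination to the sponsor side. Section 8.2 lists the events for which an individual subject must come off IFX-1.

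**The concern.** For Group 2, the written opening condition can fail in only one way: 800 mg was not considered safe and well tolerated. The next sentence responds to a Group 2 that cannot open by recruiting 6 more people to that same dose, and it is worded as an instruction, not an option. The authors made the individual dose increase at Day 57 depend on the absence of safety concerns, but put no such condition on the group-level expansion.

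Safety is the primary objective of this study, and the escalation rule is one of its main protections for subjects not yet treated. Such a rule should give the right instruction on every branch without needing to be overridden. On one branch this one does not: if 800 mg is judged unsafe, the text calls for more exposure to it.

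**Working it through.** **1. The plan's own counts.** Section 7.1.2 sets 3 groups of 6: 3 x 6 = 18, which agrees with the total in section 10.1. The 5 evaluable subjects per group give 3 x 5 = 15, which also agrees.

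**2. Doses per subject.** Section 7.1.2 gives 3 doses in the first week (Days 1, 4 and 8), then a dose every two weeks from Day 15. Section 5.2 says "the last day of dosing of IFX-1 is Day 169".

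- Two-weekly doses: (169 - 15)/14 + 1 = 11 + 1 = 12
- Total: 3 + 12 = 15

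This matches the synopsis: "All subjects will receive IFX-1 at a maximum of 15 dosing visits".

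**3. The branches of the rule.**

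| Finding after Group 1 | Group 2 | What the fallback says | Sensible? |
|---|---|---|---|
| 800 mg safe and tolerable, no other obstacle | opens | does not apply | yes |
| 800 mg acceptable, but an obstacle specific to 1600 mg | does not open | 6 more at 800 mg | yes |
| 800 mg data too equivocal to double the dose, but acceptable to continue | does not open | 6 more at 800 mg | yes |
| 800 mg judged unsafe | does not open | 6 more at 800 mg | no |

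Only the last row is at fault.

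**4. Whether another section supplies the missing condition.**

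- 8.1 and Appendix 2: powers to stop the study or close sites. They do not mention the fallback.
- 8.2: mandatory, but it applies to a subject already on treatment and does not halt recruitment to a dose.
- 9.4.9: requires an ongoing safety review, but the decision it describes is the move to the next dose group. It gives no criterion for adding subjects at 800 mg.
- 10.3.6: an interim summary that includes adverse events after each group of 6 has completed Visit V10, with no decision rule attached.

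None of these conditions the fallback.

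**5. Size on the unsafe branch.**

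- Group 1: 6 + 6 = 12 subjects
- Added infusions, ceiling: 6 x 15 = 90
- Added infusions, floor: 0, if the study is stopped

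The ceiling needs all 6 subjects to receive every dose; discontinuations under 8.2 would lower it. It is left as a count of infusions because the Day 57 condition concerns individual subjects, so some later doses could in principle be above 800 mg.

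**The case against.** The best defence is that the sentence means *cannot escalate*, not *must stop*. The wording for not opening Group 2 is wider than a finding that 800 mg is unsafe. Safe and well tolerated is a joint, graded standard that can fail on equivocal data while 800 mg stays acceptable. A problem could also surface at 1600 mg in Group 1 subjects raised at Day 57, which would block Group 2 without discrediting 800 mg. The rationale for Amendment 01 records that the study grew from 12 to a possible 18 subjects, so a Group 1 of 6 + 6 = 12 looks like a return to the smaller study if escalation fails. All of this stands, and it is why the fallback should be kept for those cases. It explains the sentence but does not limit it.

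Three stronger readings are tempting, and the documents do not support them:

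- *An unsafe 800 mg is the only thing that could trigger the fallback.* It is the only written ground for not opening Group 2, but the trigger wording admits other obstacles.
- *Only the sponsor's discretion protects the added subjects.* Section 8.1 also lets a competent authority or IRB discontinue the study or rescind its approval, and 8.2 makes stopping IFX-1 mandatory for a treated subject with unacceptable toxicity.
- *Ninety infusions is the exposure to expect.* It assumes full completion by 6 subjects on a dose already judged unsafe, which 8.2 makes implausible.

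The unsafe branch is also unlikely. Section 3.2.1 reports a 12-subject study of 9 weekly 800 mg infusions with no adverse event reported as at least possibly related. It also describes a 177-subject study, placebo included, with 800 mg every two weeks among its regimens, in which IFX-1 was well tolerated.

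**Conclusion.** The point holds, at minor severity. On the branch where 800 mg is judged unsafe, a stated rule gives the wrong instruction, and no other section qualifies it. The consequence is 6 further subjects assigned to that dose, Group 1 going from 6 to 12, with between 0 and a nominal 90 added infusions.

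This rests on reading the fallback as written and on the general safeguards acting as overrides to the rule, not as part of it. It does not imply that the sponsor would in practice expand an unsafe dose. No endpoint, analysis or estimate is affected.

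**What to change.** In both the synopsis (Treatment Groups and Duration) and section 7.1.2, make the fallback conditional. Suggested wording: *Should Group 2 not be opened, 6 additional patients will enter Group 1, provided the safety review (section 9.4.9) finds continued dosing at 800 mg acceptable; if 800 mg is judged unsafe, recruitment stops.*

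This keeps the expansion for equivocal data and for obstacles specific to 1600 mg. Stopping all recruitment on the unsafe branch fits the design, because every group begins with 800 mg on Days 1, 4 and 8, so no group avoids that dose.

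The cost is one sentence in two places at the next amendment, with no added subjects, visits or procedures. The one downside is that the sponsor commits in advance not to expand a dose it has judged unsafe.

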#### 7.1.3 Method of Treatment Assignment

On Day 1, subjects will be allocated with the next available IMP package of IFX-1 at the site. The package number will be recorded in the CRF.

#### 7.1.4 Blinding

This is an open-label study without randomization.

#### 7.1.5 Supply, storage and handling

The IMP will be supplied to study site(s) on behalf of the sponsor by Almac. Almac will provide the initial and all subsequent supplies. The initial shipment will be requested once all required site documentation is in place, including Institutional Review Board (IRB) and Regulatory Authority approvals, as well as the signed site contract(s).

The IMP must be shipped at a temperature of  $2^{\circ}$ C to  $8^{\circ}$ C ( $35.6^{\circ}$ F to  $46.4^{\circ}$ F) and should not be frozen. Each shipment will be controlled by a temperature logger, of which a read-out must be obtained by the site personnel upon receipt of the shipment.

InflaRx	Clinical Study Protocol,
	Version 4.0 Including Amendment 02, 14 May 2020
IFX-1	IFX-1-P2.7

The investigator or designee must confirm appropriate temperature conditions have been maintained during transit for all IMP received. Any discrepancies must be reported and resolved before use of the IMP.

At each study site, authorized personnel will check the IMP for any loss, damage, or tampering and confirm receipt. Records of the receipt of IMP have to be maintained.

Any technical complaints arising from defects in the quality of the IMP, or defects in the packaging or labeling of the IMP, must be reported to Almac or the sponsor at the earliest opportunity and the IMP should not be used.

The authorized personnel at each site will be responsible for receipt adequate handling, storage, dispensing and preparation of the IMP, and local drug accountability as well as recording of the accurate administration of the IMP (i.e., complete administration of IMP, including flushing of the infusion line) used for each subject.

The IMP must be stored at the site between 2°C and 8°C and should not be frozen. To record the temperature at the site, an established and validated local temperature management system with temperature logs should be used. If this is not possible, the responsible site personnel will maintain temperature records for the entire duration of the study. A template for the temperature records will be provided by the sponsor or sponsor's designee. At a minimum, the daily (working day) minimum and maximum temperatures must be documented.

Only subjects enrolled in the study may receive IMP and only authorized site staff may administer IMP. All IMP must be stored in a secure, temperature controlled, and monitored (manual or automated) area with access limited to the investigator and authorized site staff in accordance with the labeled storage conditions, separated from normal hospital inventories, and in compliance with applicable regulatory requirements.

## 7.1.6 Preparation and administration

The IFX-1 for infusion will be reconstituted (prepared) under controlled conditions at the study site or at the study site's pharmacy, in accordance with local regulations/requirements for aseptic reconstitution.

The IMP will be diluted in sterile sodium chloride. The total volume in the infusion bag for each infusion should be approximately mL.

The reconstituted IFX-1 should be used within 4 hours after dilution when stored at room temperature. Otherwise, the reconstituted IFX-1 has to be stored at

) and used within 24 hours; if the reconstituted IFX-1 solution is stored in a fridge, it must be left to acclimatize to room temperature prior to administration. Details on reconstituting the IFX-1 will be provided in the Pharmacy Manual.

InflaRx	Clinical Study Protocol,
	Version 4.0 Including Amendment 02, 14 May 2020
IFX-1	IFX-1-P2.7

The number of unused, partially used, and empty vials will be documented accurately, and the vials will be kept at the site until the drug accountability documentation has been checked by the study monitor (Section 33).

The IMP will be infused intravenously over a period of 30 to 60 minutes ( $\pm$  10 min) via an intravenous line. Sites should use the supplied intravenous lines. The infusion may be briefly (<30 min) interrupted for technical reasons, or for reinsertion of the intravenous line.

At the end of the infusion, the intravenous line will be briefly flushed with approximately 10 mL of sterile sodium chloride to ensure that any IMP remaining in the intravenous line is administered.

After each of the first 2 infusions of IMP administered, subjects must remain at the study site for at least 30 minutes after end of IMP administration; appropriate treatment for potential infusion-related reactions must be available during this time.

Each administration of IMP will be recorded in detail in the source documentation and in the CRF.

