## 7.1.8 Treatment Compliance

If a subject misses a visit or a subject appears at the study center for a scheduled infusion but the infusion cannot be administered for any reason, the visit can be repeated within 3 days and the infusion given. Otherwise, the infusion will be considered as omitted and documented accordingly in the CRF.

InflaRx	Clinical Study Protocol,
	Version 4.0 Including Amendment 02, 14 May 2020
IFX-1	IFX-1-P2.7

Subjects who omit more than 2 scheduled (consecutive or non-consecutive) infusions will be discontinued from the study and will undergo the End of Treatment visit (Visit V16) and the 2 observation visits.

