#### 9.1.4 Treatment visits (Visits V4 and V6)

- Record Dermatology Life Quality Index
- Record pain intensity using a numeric rating scale
- Document concomitant medications

- Record adverse events
- Record vital signs
- Record the Physician's Global Assessment
- Take photograph of target ulcer for area and volume measurements
- Assess target ulcer (degree of erythema and border elevation)
- Take a sample of the target ulcer fluid if wound is open and liquid is available
- Use a standard dressing and compression therapy for the target ulcer
- Take blood for
  - Safety laboratory parameters (clinical chemistry and hematology)
  - IFX-1 concentrations
  - Immunology
  - Anti-drug antibody
- Take a urine sample for urinalysis
- Perform a urine pregnancy test for a woman of childbearing potential
- Take a stool sample for the measurement of calprotectin
- Administer IMP
- Update recording of adverse events

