## 10.3.1 Safety Analyses

The primary objective of this study is to explore the safety of IFX-1 administered in subjects with pyoderma gangrenosum. Safety will be described by the following endpoints:

- TEAEs, defined as adverse events that start at or after the first administration of IMP
- Related TEAEs
- Serious TEAEs
- Adverse events of special interest

TEAEs will be analyzed according to the number and percentage of subjects who had an adverse event as well as the number of TEAEs with the respective MedDRA System Organ Class and Preferred Term. Related TEAEs and serious TEAEs will be analyzed in the same way. Additionally, the number and percentage of subjects with adverse events will be further grouped by severity and relationship. The maximum severity/relationship per subject and preferred term will be counted in these summary tables.

All safety analyses will be performed on the SAF. Analyses will generally be performed for the entire SAF as well as the 3 dosing groups separately. Additional stratifications based on actual dosing and IMP compliance will be defined in the statistical analysis plan.

InflaRx	Clinical Study Protocol,
	Version 4.0 Including Amendment 02, 14 May 2020
IFX-1	IFX-1-P2.7

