#### The following are defined as adverse events of special interest:

 Infusion-related reactions, including acute and delayed hypersensitivity and anaphylactic reactions during or after IFX-1 infusion All patients should be observed closely during the IFX-1 administration and for 30 minutes after the first 2 infusions. The IV line should remain open during the observation to allow for administration of IV drugs, if necessary. Medication for infusion-related reactions should be available for immediate use. Medical staff have to be trained in resuscitation and immediate intensive care has to be readily accessible in case of severe life-threatening events. Mild to moderate reactions may be treated by slowing or interruption of the infusion, or with supportive treatment. For any potential infusion-related event, the investigator should check for a potentially developing or existing anaphylactic reaction. If an anaphylactic reaction is possible, appropriate immediate actions should be taken according to the severity or stage of the detected anaphylactic reaction as recommended by existing guidelines for the treatment of anaphylactic reactions or, if established at the study sites, according to available standard operating procedures or other algorithms.

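### As scheduled, the required 30-minute stay after infusion covers only two 800 mg infusions; the first infusion at 1600 or 2400 mg has no required minimum time on site

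*Combined protocol and SAP*

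**What the plan says.** - **Required stay.** Section 7.1.6: "After each of the first 2 infusions of IMP administered, subjects must remain at the study site for at least 30 minutes", with treatment for reactions available during that time. Appendix 3, under adverse events of special interest: "All patients should be observed closely during the IFX-1 administration and for 30 minutes after the first 2 infusions".
- **Doses.** Section 7.1.2: "All subjects will receive IFX-1 800 mg three times during the first week (Days 1, 4, and 8"). From Day 15, dosing is every two weeks at 800 mg (Group 1), 1600 mg (Group 2) or 2400 mg (Group 3). At V7 (Day 57), a Group 1 or 2 subject may move up one level if the Physician's Global Assessment is 4 or more and nothing speaks against it on safety.
- **Infusion time.** Section 7.1.6: "The IMP will be infused intravenously over a period of 30 to 60 minutes", with a 10-minute tolerance either way and no link to dose.
- **Later infusions.** Sections 9.1.3 (V7) and 9.1.4 (V4) follow dosing with the step "Update recording of adverse events", without a time.
- **Omissions.** Section 7.1.8: "Subjects who omit more than 2 scheduled (consecutive or non-consecutive) infusions will be discontinued from the study". Up to two omissions are therefore tolerated.

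**The concern.** The stay is tied to the infusion count, not to the dose. It is used up before any scheduled dose increase. Infusion-related reactions, including those starting after the infusion, are an adverse event of special interest and so part of the primary endpoint. Section 3.3.2 relies on treatment at the study site as the safeguard against anaphylaxis, and that works only while the subject is there. A reaction beginning soon after a first 1600 or 2400 mg infusion could be managed less promptly than one after the first two 800 mg infusions. The earlier human experience summarised in the protocol does not reach these doses.

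**Working it through.** **Calendar.** Infusions fall on Days 1, 4 and 8, then on Day 15 + 14k for k = 0 to 11.
- Count: 3 + 12 = 15, matching the 15 dosing visits in the synopsis.
- V4 (k = 0) is Day 15. V7 (k = 3) is 15 + 42 = Day 57, as in 7.1.2. V15 (k = 11) is 15 + 154 = Day 169, as in 5.1 and 5.2.

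**Doses under the required stay, all subjects fully dosed.**

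| Group | Infusions 1 and 2 | First higher dose | Second step |
|---|---|---|---|
| 1 | 800, 800 mg | V7: 1600 mg, if increased | none |
| 2 | 800, 800 mg | V4: 1600 mg | V7: 2400 mg, if increased |
| 3 | 800, 800 mg | V4: 2400 mg | none |

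Required stays now: 18 × 2 = 36 of 18 × 15 = 270 planned infusions, all at 800 mg. First infusions at a higher level: 6 + 6 = 12 at V4, plus 0 to 12 at V7, so 12 to 24. One exception exists: a subject who omits both Day 4 and Day 8 has V4 as the second infusion given, and so gets the stay there.

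**Earlier experience (3.2.1).** The highest flat dose is 1200 mg: 1600/1200 = 1.33 and 2400/1200 = 2. The highest weight-based dose, 8 mg/kg, reaches 1600 mg only at 1600/8 = 200 kg.

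**Infusion rate.** Over 60 to 30 minutes:
- 800 mg: 13.3 to 26.7 mg/min
- 1600 mg: 26.7 to 53.3 mg/min
- 2400 mg: 40 to 80 mg/min

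At equal duration the rate doubles or triples. Duration may vary, however: 1600 mg over 60 minutes matches 800 mg over 30, and 2400 mg over 60 minutes is 40/26.7 = 1.5 times it. If 800 mg was run over 60 minutes, even 70 minutes (the upper tolerance) gives 2 × 60/70 = 1.7 times for 1600 mg and 3 × 60/70 = 2.6 times for 2400 mg.

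**V7 against the group-start gate (9.4.9).** Group 3 needs safety data from at least 5 patients on 1600 mg for at least 1 month. A Group 2 subject reaches V7 57 − 15 = 42 days after starting 1600 mg. Assume 1 month is 30 days and only Group 2 subjects count. The first subject's V7 then precedes the gate if the fifth subject starts 1600 mg more than 42 − 30 = 12 days after the first. Neither 7.1.2 nor 9.4.9 ties the V7 increase to the gate, so an individual increase may be the first use of 2400 mg in the trial. An increased Group 1 subject could likewise be the first on 1600 mg.

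**The case against.** The strongest reply is that this is a preference about clinical practice.
- Higher doses are gated: 9.4.9 requires safety data before each group opens, and 7.1.2 bars an increase at V7 if there are safety concerns.
- In the simulation in 3.2.3, at 2400 mg every two weeks only 0.3% and 0.1% of patients exceed the NOAEL values for AUC and Cmax.
- Section 3.3.2 attributes the anaphylaxis risk to the product being a protein, which suits a stay at first exposures. A fully dosed subject has had three infusions before V4 and six before V7, and 8.2 stops treatment after a serious allergic reaction.
- Section 3.3.2 reports no anaphylactic reactions to date, and 3.2.1 reports similar adverse events across the groups of the 400 to 1200 mg study.
- The limit may be deliberate: the Appendix 3 text came in with the amendment that introduced the higher doses.

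These points keep the gap small. They do not close it. The gate governs group starts, not individual increases at V7. The clinical reports summarised do not cover 1600 or 2400 mg. No visible text explains why two stays suffice. The investigator's brochure, the pharmacy manual and the Schedule of Assessments grid could not be consulted.

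Two stronger readings are tempting. A reader might infer that higher-dose infusions go unobserved. They do not: Appendix 3 requires close observation during every infusion, medication at hand and trained staff. A reader might also infer that the rate must double or triple. It does so only at unchanged duration, and the permitted range lets sites offset part of the increase. Appendix 3 does treat rate as relevant to an ongoing reaction ("Mild to moderate reactions may be treated by slowing or interruption of the infusion"), but that says nothing about time on site afterwards.

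**Conclusion.** The point holds as a modest patient-safety gap with an inexpensive remedy. As scheduled, none of the 12 to 24 first infusions at a higher level has a required stay. These counts are maxima: they assume that Groups 2 and 3 both open and fill, and that every subject is still being dosed at V4 and V7.

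A reader might go further and infer that reactions rise with dose, or that the planned safety tables are biased. The documents support neither. They give no reaction rates or timings, and every group currently has its required stays at the same two infusions. The benefit of a 30-minute stay at the new doses is a clinical judgement that extends the protocol's own precaution.

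**What to change.** In 7.1.6 and Appendix 3, also require the stay of at least 30 minutes, with reaction treatment available, after the first infusion actually given at each higher dose level. Tying it to the infusion given, not to a visit number, covers an omitted V4 or V7. The clinical team should confirm the duration.

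**Cost.** At most 12 to 24 extra stays: 12 × 0.5 = 6 hours to 24 × 0.5 = 12 hours across the trial. The text change is one sentence in each place. It is still a protocol amendment needing IRB approval and an updated consent form (Appendix 2), so it is best combined with the next amendment. No analysis changes.

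**Option.** The dose-tied rule gives 2 stays per subject in Group 1 (3 if increased), 3 in Group 2 (4 if increased) and 3 in Group 3. Section 10.3.1 says: "Analyses will generally be performed for the entire SAF as well as the 3 dosing groups separately". If equal observation across those tables is wanted, apply the stay at V4 and V7 in all groups, or at the next infusion given if one is omitted. That is 18 × 2 = 36 added stays (18 hours) and 4 per subject throughout. Of the 36, 12 to 24 would serve only balance, which is hard to insist on in a descriptive open-label study.
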